### **Serious Adverse Events**

An event that is serious will be recorded on the Serious Adverse Event log. SAEs will be recorded from the signing of informed consent hospital discharge.

The most common adverse events are mild and related to underlying disease such as respiratory distress. If these occur, they will be noted in the adverse event tracking log and reported to the IRB during Continuing Review.

More serious adverse events and any unexpected adverse events will be recorded as per UM HSRO policies and procedures.

### **Disease Related Adverse Events**

It is recognized that this patient population who require critical care support will experience a number of common aberrations in laboratory values, signs, and symptoms due to the severity of the underlying disease and the impact of standard therapies. These will not necessarily constitute an AE unless they require significant intervention, lead to discontinuation of study medication, felt to be related to study medication or are considered to be of concern, in the Investigator's clinical judgment. Examples of the type of AEs that may be associated with the patient population are listed below.

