**3) Inclusion and Exclusion Criteria\***

INCLUSION CRITERIA:

- a. >18y of age,
- b. Subject or proxy who can provide informed consent
- c. Positive SARS COV2 by PCR or as determined by clinical team

EXCLUSION CRITERIA:

- a. Adults or Proxy unable to consent
- b. Individuals who are not yet adults (infants, children, teenagers)
- c. Pregnant women
- d. Prisoners
- e. Patients expected to die within 24 hours or with a “do not resuscitate” order,
- f. Multi-organ failure,
- g. History of hypersensitivity or allergy to any component of the study drug,
- h. Ongoing massive surgical or unexplained bleeding,
- i. History of bleeding or clotting disorder,
- j. Severe traumatic brain injury (Glasgow Coma Scale <6),
- k. Spinal or multiple-trauma,
- l. Cancer (incurable/terminal phase) and/or patients receiving palliative care,
- m. Enrollment in another concurrent clinical interventional study
  - if considered interfering with this study objectives
- n. Per study team discretion, any condition(s) that may prevent safe treatment, preclude adequate evaluation or adding further risk to their underlying illness.

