### **List of Expected Adverse Events**

Acute respiratory failure; respiratory distress; acute lung injury; acute respiratory distress syndrome (ARDS); acute renal failure; coagulation dysfunction; decreased platelets count; neutropenia; hypothermia; fever, bacteremia; sepsis, septic shock; hypotension; metabolic acidosis, pleural effusion; abdominal compartment syndrome; repeated surgeries/debridement; amputation.

For purposes of this study, deaths will be captured as clinical outcomes and do not need to be reported as SAEs unless felt related to study drug administration.

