**13) Risks to Subjects\***

Hypersensitivity reactions, including anaphylaxis, are possible. Should symptoms occur, THROMBATE III infusion will be discontinued and appropriate treatment begun as per clinical judgement.

- Because THROMBATE III is made from human blood, it may carry a risk of transmitting infectious agents, e.g., viruses, the variant Creutzfeldt-Jakob disease (vCJD) agent and, theoretically, the Creutzfeldt-Jakob disease (CJD) agent.
- We will perform coagulation tests to avoid excessive or insufficient anticoagulation and monitor for bleeding or thrombosis. Assessment will be based on clinical findings at the discretion of the treating physician along with laboratory values of PT, PTT, Hemoglobin and Hematocrit analysis. Treatment may include heparin for excessive coagulation or blood transfusion for insufficient coagulation ultimately left to the discretion of the treating physician.

Two clinical trials were conducted in 33 subjects with congenital AT deficiency. Nine subjects (27%) experienced 29 adverse reactions which occurred during 17 of 389 infusions. There were no serious adverse reactions reported. The severity of adverse reactions was reported as mild or moderate, except for wound secretion and hematoma, which was severe.

Dizziness (12%), Chest discomfort (9%), Nausea (9%), Dysgeusia (6%), Pain (cramps) (6%), and each of the following were reported in 3% of the subjects: Chills, Wound secretion and hematoma, Vision blurred, Chest pain, Dyspnea, Intestinal dilatation, Pyrexia and Urticaria,

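### Two of the four routes by which a disease-related sign becomes an adverse event are open only to the AT3 arm, so AE-log counts are not collected by one rule across groups

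*Combined protocol and SAP*

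**What the plan says.** Section 10, Disease Related Adverse Events, accepts that critically ill patients will show many abnormal signs and laboratory values, and sets a filter: "These will not necessarily constitute an AE unless they require significant intervention, lead to discontinuation of study medication, felt to be related to study medication". The sentence goes on to a fourth route, events that "are considered to be of concern, in the" investigator's clinical judgement. The list that follows includes fever and respiratory distress.

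Other parts of the protocol bear on the same events:

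- Section 10, Serious Adverse Events: "The most common adverse events are mild and related to underlying disease such as respiratory distress". It then says that these are entered in the AE tracking log and reported to the IRB at Continuing Review.
- Section 10, An AE does not include: the studied disease and its signs are left out, except where the disease worsens.
- Section 10, Relationship to Study Medication: three levels only (unrelated, probable, definite). Probable requires, among other things, that the clinical state is an unlikely explanation and that the event improves when the drug is stopped.
- Section 10, Procedures for Reporting Adverse Events: AE recording runs from consent to the last dose of study drug.
- Section 13: reactions seen in 3% of subjects each include "Chest pain, Dyspnea, Intestinal dilatation, Pyrexia and Urticaria".
- Section 8: all groups are followed for adverse events.
- Section 12: two infusion reactions pause the study. The term is not defined.

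**The concern.** Whether an event counts as an AE should not depend on the arm. Here two of the four routes, "lead to discontinuation of study medication, felt to be related to study medication", presuppose that the patient is on study medication. The same hypotensive episode could become an AE in the AT3 group because the investigator links it to an infusion, and stay off the log in a control. Because the trial is open label (Section 1), the person applying the filter knows the group.

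Relationship is also normally judged for an event already recorded. Here it partly decides whether the event is recorded. Where a listed disease sign looks like a drug reaction, a wrong attribution can remove the event rather than merely mislabel it. At stake are the comparability of AE tables between the randomised groups and, less directly, the completeness of the information behind the infusion-reaction pause.

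**Working it through.** The plan gives no AE rate, target or power calculation to reproduce. The check is mainly textual, with some arithmetic on the Section 13 figures.

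**1. Routes by group.** Section 4 gives three groups of 25. Only the third receives AT3.

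| Route to AE status | AT3 ≥100%, standard care | AT3 <100%, standard care | AT3 <100%, plus AT3 |
|---|---|---|---|
| Significant intervention needed | yes | yes | yes |
| Study medication discontinued | no | no | yes |
| Felt related to study medication | no | no | yes |
| Of concern to investigator | yes | yes | yes |

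Two of the four routes are closed to 25 + 25 = 50 of 75 patients, including all 25 randomised controls. The recording window has the same fault: a last dose does not exist in those 50 patients.

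**2. Passages side by side.** Take mild respiratory distress that needs no significant intervention. Serious Adverse Events says it is logged. Disease Related Adverse Events allows it to be left out. If it is a worsening of COVID-19, An AE does not include makes it an AE. Site staff cannot follow all three.

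**3. Overlap with drug reactions.** With n = 33, the Section 13 percentages correspond to these numbers of subjects: 12% = 4, 9% = 3, 9% = 3, 6% = 2, 6% = 2, and eight terms at 3% = 1 each. The total is 4 + 3 + 3 + 2 + 2 + 8 = 22 subject-level reports. Section 13 separately counts 29 reactions, so the 22 are not episodes. Fever matches pyrexia directly (1) and respiratory distress matches dyspnea closely (1): 2/22 = 9%. Chest discomfort and chills are not on the expected list. Hypotension is on the list but is not a named reaction.

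**4. Possible size of unequal capture (illustration).** Assume equal true risk in both randomised groups. Let c be the share of listed signs caught by the two common routes, and e the share of the rest caught by the two drug-only routes. Then

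recorded ratio, AT3 to control = [c + (1 − c)e] / c = 1 + (1 − c)e/c.

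- c = 0.5, e = 0.2: 1 + 0.5 × 0.2/0.5 = 1.20. With an assumed true risk of 60%, that is 9.0 against 7.5 patients of 25.
- c = 0.3, e = 0.3: 1.70.
- c = 0.7, e = 0.3: 1.13.
- e = 0: 1.00.

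The values of c, e and the 60% are assumptions; the documents give none. Misattribution works the other way: true drug reactions read as disease are lost, which understates any real excess.

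**5. Pause rule (illustration).** Assume that the Section 13 rate applies here (17/389 = 4.37% of infusions), that infusions are independent, and that the pause count relies on recorded reactions. The maximum is 25 patients × 5 doses = 125 infusions. The expected number with a reaction is 125 × 0.0437 = 5.5.

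| Share recorded | P(at least 2), 125 infusions | P(at least 2), 75 infusions |
|---|---|---|
| 100% | 0.975 | 0.845 |
| 91% (20/22, only the overlap lost) | 0.961 | 0.804 |
| 50% | 0.760 | 0.490 |
| 25% | 0.397 | 0.198 |

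If only reactions of the overlapping kinds were lost, the effect would be small. It becomes material only under much heavier loss, which the documents do not establish.

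**The case against.** The filter is permissive rather than an exclusion, and its four routes are alternatives. Significant intervention and investigator concern apply in every group and should catch most events that matter. A recognised reaction passes as drug-related, or because the drug is stopped: Section 13 says the infusion is discontinued if hypersensitivity symptoms appear. The AE definition also includes signs first detected after study drug is given. The Section 12 triggers are worded as events, and nothing ties them to the AE log. No between-arm AE comparison is planned in Sections 7 or 9 or Appendix C. Mortality, VTE and major bleeding are captured as outcomes for all groups. Platelets, PT, PTT, anti-Xa and vital signs are scheduled for everyone (Appendix B), so a platelet fall is measured whatever its AE label.

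Most of this stands, and it limits the point to AE-log counts. It does not remove the asymmetry: Section 8 has all groups followed for adverse events, and any later table of those events by arm will inherit the unequal rule.

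A reader might infer that infusion reactions as a class go unrecorded. The text does not support that. An event is lost only if it is attributed to COVID-19, needs no significant intervention and raises no concern. A reader might also infer that an amputation would disappear because the expected list contains "repeated surgeries/debridement; amputation". It would pass as a significant intervention in any arm. Those items sit oddly in a cohort that excludes "Spinal or multiple-trauma", but that is a matter of tidying.

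**Conclusion.** The point holds in limited form. Two of the four routes to AE status can be met only in the AT3 group, so AE-log counts in the two randomised groups come from different rules. The passage also contradicts the logging statement under Serious Adverse Events and the disease-worsening rule under An AE does not include.

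The size of any distortion cannot be derived from the documents. Under the assumed capture shares, the recorded ratio runs from 1.00 to 1.70 with no true difference. It would be tempting to call the AE comparison biased in a stated direction; the documents do not support that, because the extra routes raise the AT3 count while misattribution hides real reactions. The textual overlap with known reactions is narrow: 2 of about 22 reports (9%), counting dyspnea as equivalent to respiratory distress. The loss of a misattributed reaction is possible, helped by a relationship scale with no level below probable, but it is not shown to be likely.

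The change is worth making before AE data are tabulated by arm.

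**What to change.** 1. Merge the three conflicting parts of Section 10 (An AE does not include, Serious Adverse Events, Disease Related Adverse Events) into one recording rule that does not refer to study medication. Use the same severity threshold in all three groups. If it is set above mild, amend the sentence that sends mild disease-related events to the log.
2. Replace the last-dose end of AE recording with one study-day window for all groups, and align the Appendix B footnote.
3. Record relationship to study drug and drug discontinuation as separate fields, completed after the event is entered and with no say in whether it is entered.
4. Keep a separate infusion-reaction listing for the AT3 group, flagging listed signs that start during an infusion or within a stated period after it, whatever their attribution. Use it for the Section 12 pause rule, with a written definition of the term, and keep it out of the between-arm AE counts. Merging it with those counts would bring back a rule that applies to one arm only.

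Removing the surgical items from the expected list is optional. The cost is protocol and AE-log wording, plus somewhat more entries in a sick population.

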### **List of Expected Adverse Events**

Acute respiratory failure; respiratory distress; acute lung injury; acute respiratory distress syndrome (ARDS); acute renal failure; coagulation dysfunction; decreased platelets count; neutropenia; hypothermia; fever, bacteremia; sepsis, septic shock; hypotension; metabolic acidosis, pleural effusion; abdominal compartment syndrome; repeated surgeries/debridement; amputation.

For purposes of this study, deaths will be captured as clinical outcomes and do not need to be reported as SAEs unless felt related to study drug administration.

### **11) Withdrawal of Subjects\***

The occurrence of any of the following events may necessitate premature withdrawal of a subject from the study:

- Development of any of the following Inclusion/Exclusion criteria:
  - Subjects with a "do not resuscitate" order,
  - Multi-organ failure,
  - History of hypersensitivity or allergy to any component of the study drug,
  - Ongoing massive surgical or unexplained bleeding,
  - History of bleeding or clotting disorder,
- Occurrence of a serious adverse event (SAE) thought to be related to study drug and not alleviated by symptomatic treatment
- Unwillingness to continue in the clinical study
- Death of the subject
- Principal Investigator decision (i.e. subject non-compliance with study procedures)
- Significant AE or medical decision that precludes the subject from adhering to study requirements

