**2) Background\***

Coronavirus disease 2019 (COVID-19) is an infectious disease caused by severe acute respiratory syndrome coronavirus 2 (SARS-CoV-2). As of 6/24/20, as social distancing was easing, the U.S. recorded >2.3M COVID-19 infections and >121K deaths, with new cases rising in at least 27 states [<https://coronavirus.jhu.edu/map.html>]. Worldwide, cases are rising at an even more alarming pace; there were 1M on 4/1/20, and >9.2 M cases with 478K deaths by 6/24/20. [<https://coronavirus.jhu.edu/map.html>].

A unique feature of the acute respiratory distress syndrome (ARDS) associated with COVID is a relatively preserved lung compliance and acute inflammation associated with a high alveolar-arterial oxygen gradient [PMID: 32267998]. The pathogenesis involves a rapid increase in airway cytokines which promotes pulmonary leukocyte sequestration, further propagating the local inflammatory response. Fibrin is deposited in the air spaces and lung parenchyma with elevated D-dimers and fibrinogen. Tissue factor (TF) is exposed on damaged alveolar endothelial cells and on the surface of leukocytes promoting more fibrin deposition, while increasing plasminogen activator inhibitor 1 (PAI-1) from lung epithelium and endothelial cells which creates a hypofibrinolytic state [PMID: 32329246]. The signature finding on autopsy is diffuse pulmonary microthrombi associated with an ARDS caused by vascular occlusion rather than the more classic findings of low-compliance [PMID: 32267998].

The most severely ill patients often present with mild symptoms that rapidly progress within 12-24h to multi-system involvement including ARDS, myocarditis, arrhythmias, cardiac arrest, gastrointestinal symptoms, hypoxic brain injury, acute liver, renal function impairment, and cutaneous lesions. The common link seems to be microvascular occlusion with thrombi or viral laden antigen-antibody immune complexes [PMID: 32559324].

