**8) Procedures Involved\***

Any member of the study team will discuss potential subjects with the clinical team for appropriate pursuit of informed consent and screening for eligibility.

75 eligible subjects, after consent, will have laboratory blood tests for further screening.

25 of those subjects with endogenous **AT3  $\geq$  100%** will continue with SOC.

50 of those subjects with endogenous **AT3 < 100%** will be will be randomly assigned to begin **SOC plus treatment with exogenous AT3 supplementation or only SOC** treatment. The randomization schedule will be established by a member of the study team that is not involved in the informed consent process.

They will all be followed up for laboratory blood tests, study endpoints and adverse events. If they do not meet entry criteria they will be excluded from the study.

[figure not shown]
Consented subjects will be scored according to The International Society of Thrombosis and Haemostasis Disseminated Intravascular Coagulation scale (ISTH DIC) on study visit days 1, 3, 5, 7, 9 and 11.

The SOFA score will be performed only when the parameter is obtained clinically and monitored for changes in patient status on study visit days 1, 3, 5, 7, 9 and 11. Each organ system is assigned a point value from 0 (normal) to 4 (high degree of dysfunction/failure). It will be calculated on admission and Day 11 using the worst parameters measured during the study visit day. If a parameter is not obtained clinically it will be voided for research purposes.

UM IRB# 20201048

AT3 in COVID-19  
January 24, 2022, Version 6.2

After enrollment and each 48h period (+/- 12 hours) thereafter, blood samples are collected and assayed for routine clinical coagulation and inflammation markers, including AT3 activity, D-Dimer, anti-Xa, fibrinogen, and prothrombin time until Day 11.

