### Appendix C

The Secondary endpoint measurements:

- a. D-dimer level change from baseline to Day 9 in mcg/mL FEU or DDU,
- b. Fibrinogen level change from baseline to Day 9 in mg/dL
- c. Prothrombin time change from baseline to Day 9 in seconds
- d. Length of hospital stay in days,
- e. Mortality (%) of overall and between groups,
- f. Pulmonary function
  - a. Time (days) to mechanical ventilation and/or
  - b. ECMO Duration (days) or extracorporeal membrane oxygenation (ECMO) use,
- g. SOFA score change from baseline to Day 9 and
- h. SOFA Respiratory sub-score change from baseline to Day 9,
- i. Number of venous thromboembolisms from admission to hospital discharge,
- j. Number of major bleeding events from admission to hospital discharge

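### Section 11 lets patients leave the study, not only the study drug, on events tied to the endpoints; with no follow-up or analysis rule, the AT3 versus standard-of-care contrast can be biased in either direction

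*Combined protocol and SAP*

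**What the plan says.** Section 11 (Withdrawal of Subjects) opens with events that "may necessitate premature withdrawal of a subject from the study". Under the development of entry criteria it lists a DNR order, "Multi-organ failure", drug hypersensitivity, "Ongoing massive surgical or unexplained bleeding" and "History of bleeding or clotting disorder". Separate items are a drug-related SAE that symptomatic treatment does not relieve, unwillingness to continue, death, "Principal Investigator decision (i.e. subject non-compliance with study procedures"), and a significant AE or medical decision that prevents adherence.

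Other relevant text:

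- Section 7 sets the primary endpoint as the change in ISTH DIC score to Day 9. Appendix C adds SOFA change to Day 9, mortality, VTE, and "Number of major bleeding events from admission to hospital discharge".
- Section 2 says the most severely ill often present with mild symptoms that "rapidly progress within 12-24h to multi-system involvement". Section 3 excludes multi-organ failure at entry, so any later case is deterioration on study.
- Section 8 says of enrolled patients: "They will all be followed up for laboratory blood tests, study endpoints and adverse events".
- Section 9 imputes missing continuous values by methods it does not name. It gives no rule for withdrawn or dead patients and no as-randomised analysis set.
- Section 7 classes early discharge as a success. There is no matching rule for an early bad exit.
- Section 10 records SAEs to discharge and captures deaths as clinical outcomes.
- Section 1 describes the trial as open label.

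**The concern.** A patient who must stop study drug can still give a Day 9 score. A patient who leaves the study may not. Multi-organ failure is close to SOFA worsening, massive bleeding to the major-bleeding count, and a DNR order to death, so the patients most likely to go are those with the worst values.

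The loss may also differ by arm. A drug-related SAE can arise only in infused patients, and the same is true in practice of study-drug hypersensitivity. The rule is discretionary and is applied by people who know the allocation.

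At stake is the one randomised comparison, 25 versus 25. If the Day 9 score is missing because the patient deteriorated, analysis alone cannot reliably restore it.

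**Working it through.** **The plan's own figures.** Section 4 gives 3 × 25 = 75, of whom 50 are randomised. No effect size, SD, dropout rate or withdrawal rate is stated, so there is no planned figure to reproduce. Section 7 expects 10-20% all-cause morbidity: 0.10 × 50 = 5 to 0.20 × 50 = 10 randomised patients. That is not a rate of Section 11 events; it only sets a scale.

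**Illustration (assumed, not in the documents).** Progressors change by +3 DIC points and everyone else by -1. The Appendix A items allow a score of 0 to 2 + 1 + 2 + 3 = 8, so such changes are possible. Suppose 5/25 SOC and 2/25 AT3 patients progress (7/50 = 14% overall). The contrast is AT3 minus SOC; negative favours AT3.

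- SOC, all kept: (5 × 3 + 20 × (-1))/25 = -0.20
- AT3, all kept: (2 × 3 + 23 × (-1))/25 = -0.68
- An arm that loses all its progressors: -1.00

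| Who leaves (completers analysed) | SOC | AT3 | Contrast |
|---|---|---|---|
| Nobody | -0.20 | -0.68 | -0.48 |
| All progressors, both arms | -1.00 | -1.00 | 0.00 |
| SOC progressors only | -1.00 | -0.68 | +0.32 |
| AT3 progressors only | -0.20 | -1.00 | -0.80 |

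**No true effect** (5/25 in each arm): the true contrast is 0. If only SOC progressors leave it is -0.20 - (-1.00) = +0.80; if only AT3 progressors leave it is -0.80.

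**True harm** (2/25 SOC, 5/25 AT3): the true contrast is -0.20 - (-0.68) = +0.48. If all progressors leave it is 0. If only AT3 progressors leave it is -1.00 - (-0.68) = -0.32, a false benefit.

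**Partial withdrawal.** With event rate p and a share w of event patients withdrawn, the arm mean is [3p(1 - w) - (1 - p)] / [p(1 - w) + (1 - p)]. Take p = 0.20 (SOC) and 0.10 (AT3).

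- w = 0: -0.60 - (-0.20) = -0.40
- w = 0.5 in both arms: SOC (0.30 - 0.80)/0.90 = -0.556; AT3 (0.15 - 0.90)/0.95 = -0.789; contrast -0.23
- w = 1 in both arms: 0.00

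**Check with a continuous outcome.** Take a normal change, SD 1, and withdraw values above a common cut-off c. The retained mean is μ - φ(c - μ)/Φ(c - μ). A true -0.50 SD becomes -0.39 when 10% of controls are withdrawn and -0.33 when 20% are. In both models, the same rule in both arms shrinks a benefit without reversing it. Reversal needs withdrawal that depends on arm.

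**Imputation.** If each missing score is filled with its arm's completer mean (-1.00), the result is again 0. A method using the patient's own earlier DIC scores might recover part of the effect. The plan does not say which applies.

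**Precision (secondary).** Assuming two-sided 0.05 and 80% power, the detectable effect is (1.96 + 0.84) × √(2/n): 0.79 SD at 25 per arm and 0.89 SD at 20.

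**The case against.** The strongest reply is that the rule is permissive, no withdrawal rate is given, and much outcome capture exists elsewhere. Section 6 allows record-based follow-up after the last draw, Section 10 records SAEs to discharge and deaths as outcomes, Section 12 pauses the study on any major bleed, and Appendix B collects mortality, VTE and bleeding at discharge. This largely stands for the discharge outcomes. An event that triggers withdrawal has already happened and can be counted, so only later events are at risk. But none of these provisions says it continues after withdrawal, and none supplies a missing Day 9 score.

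Section 9 also plans imputation, so completer analysis is not the stated method. That is fair, and the loss of the whole effect is an extreme case. An unnamed method is still no assurance.

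Section 9 further compares fastest with slowest recovery halves and sets out no arm comparison of the primary endpoint. That is true, but the trial randomises 25 versus 25, and a patient without a Day 9 change cannot be placed in a half either, except by imputation.

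A reader might infer more than the documents support:

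- *That the contrast will shrink or reverse.* Shrinkage follows if AT3 works and both arms lose progressors alike; reversal, exaggeration and masked harm need unequal loss. The documents do not settle which applies.
- *That Section 11 contradicts Section 8.* It can be read as an exception to the general follow-up statement. The two should be reconciled, but it is not a flat contradiction.
- *That the clotting-disorder item means VTE or a rising DIC score.* The text says history of such a disorder, and no section defines it that way.
- *That investigator decision is unlimited.* The item is glossed as non-compliance, although the separate medical-decision item is broader.

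**Conclusion.** The concern holds as a risk of bias of unknown direction. Section 11 permits withdrawal from the study on events closely tied to the endpoints, for drug-related events confined to the infused arm, and by judgement in an open-label trial. No follow-up or analysis rule covers those who leave.

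In the illustration a true -0.48 DIC points can appear as anything from -0.80 to +0.32, with 0 if every progressor leaves both arms. These figures rest on assumed changes of +3 and -1, assumed event splits, complete withdrawal of the progressors concerned, and completer analysis. With half of event patients leaving both arms, the movement is smaller (-0.40 to -0.23). The size in this trial cannot be derived from the documents.

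The Day 9 DIC and SOFA changes are the most exposed; bleeding, VTE and mortality are exposed only for events after withdrawal. It is worth correcting before data are lost, because the remedy is cheap.

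**What to change.** In Section 11:

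1. Separate stopping study drug from withdrawal from the study.
2. State that patients with any listed clinical event stay in follow-up in their randomised group, with scheduled DIC, SOFA and laboratory data to Day 11 and outcomes to discharge, unless consent is withdrawn.
3. Remove death from the withdrawal list, to agree with Section 10.
4. If investigator-decision withdrawal is kept, record its reason and date by arm.

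In Section 9, specify an as-randomised analysis. Name in advance how death before Day 9 and any remaining missing Day 9 scores are handled, with a sensitivity analysis for outcome-related loss. Retention alone does not give a patient who dies a Day 9 score, so this step is needed too.

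The cost is protocol wording and a few more research draws in very ill patients; most of the data are routine. This takes no position on when study drug should be stopped.
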